11.7.2.2. Handling of Missing Data for Statistical Analysis

Endpoints measured at specific visits and analyzed in terms of visit numbers include: IPSS, prostate volume, Qmax, PSA, post void residual volume, BPH Impact Index (BII), BPH-Related Health Status, and PAS-SFI. Analysis of the data collected in terms of visit numbers will be performed using two different approaches to account for missing data.

1. LOCF (Last Observation Carried Forward) analysis: This involves bringing (carrying) forward the last non-missing post-baseline assessment for subjects with missing visit data and/or for subjects who discontinued from the study.
2. At Visit analysis: Missing values at post-baseline assessments are not replaced and are regarded as missing.

The LOCF approach will be considered primary for those endpoints in which both LOCF and At Visit are used. If the LOCF and At Visit results are not consistent with regard to the statistical analyses and conclusions, then further data analyses will be undertaken.

11.7.3. Questionnaire Total Score Imputation

Calculations of IPSS total and BII total, including imputation for missing responses, are described in the respective RAP sections.

11.8. Appendix 8: Adverse Event Time Periods and Special Adverse Event Definitions

Date-related derivations and transformations related to adverse events (AEs) are described below.

AE Onset Time since First Dose

= AE Onset Date – Treatment Start Date if treatment start date > AE onset date
= AE Onset Date – Treatment Start Date +1 if treatment start date <= AE start date
= missing otherwise

AE Duration (in days) = AE Resolution Date – AE Onset Date + 1

The timing of AEs will be categorized as follows:

- An AE is “Pre-Treatment” if the AE onset date is before the treatment start date.
- An AE is “On Treatment” if the AE onset date is on or after the treatment start date (but on or before the treatment stop date, if that is non-missing), or if the onset date is missing.
- An AE is “Post-Treatment” if the treatment stop date is non-missing, and the AE onset date is after the treatment stop date.
- An AE is “Post-Randomization” if the AE is either On Treatment or Post-Treatment.

Note: Cut-off dates are defined in [Appendix 6](#); definition is repeated here, in terms of 6-month treatment periods, since this is used to determine AE onset period:

Month k Cut-off Date (for k= 6, 12, 18, 24): The maximum of [Month k clinic visit date, Month k lab visit date, Baseline Date + (k * 91/3)].

An on-treatment AE is uniquely identified as having onset within one of the following four time periods: Months 1-6, Months 7-12, Months 13-18, or Months 19-24.

- An AE is considered to have onset in the Months 1-6 time period if it is an on-treatment AE and the onset date is on or before the Month 6 cut-off date.
- An AE is considered to have onset in the Months 7-12 time period if it is an on-treatment AE and the onset date is after the Month 6 cut-off date and is on or before the Month 12 cut-off date.
- An AE is considered to have onset in the Months 13-18 time period if it is an on-treatment AE and the onset date is after the Month 12 cut-off date and is on or before the Month 18 cut-off date.
- An AE is considered to have onset in the Months 19-24 time period if it is an on-treatment AE and the onset date is after the Month 18 cut-off date.

If the AE onset date is partially missing, the timing is determined as follows:

1. If the non-missing parts of the date (either just year or year/month) are unambiguously before the start of treatment, the AE is considered Pre-Treatment.

2. If the non-missing parts of the date are unambiguously after the stop of treatment, the AE is considered Post-Treatment.
3. If #1 or #2 above cannot be assigned, then the AE is considered On-Treatment.

If an on-treatment AE onset date is partially missing, then, for the purpose of assigning the 6-month treatment period referenced above, the onset date will be imputed according to the algorithm described in the second paragraph below, and the imputed date will be used to assign the period.

An AE is considered drug-related if the relationship variable indicates so, or the variable value is missing. When an AE has an outcome of Resolved/Recovered with or without sequelae, it may be categorized for resolution status as follows: if resolution date is on or before treatment stop date, the AE is considered resolved on-therapy, or if either the resolution date or the treatment stop date is missing and the action taken is not 'investigational product withdrawn', the AE is considered resolved on-therapy. If a resolved AE is not resolved on-therapy, it is considered resolved off-therapy.

For the purpose of Kaplan-Meier estimates for Special Interest AEs, and for categorizing AEs by time intervals, the following algorithm will be used:

- 1) If an AE start date is partial, it will be imputed as follows:
 - a. If all components of the date (day, month and year) are missing, then the date will not be imputed, but the AE will be categorized in the first 6-month time period.
 - b. If both day and month are missing, then the day and month will be imputed as 01 January.
 - c. If only day is missing, then the day will be imputed as 01.
 - d. Any imputation described in items 1b and 1c above will be revised if it is in conflict with the treatment start date: if the month and year of treatment start date is same as those in the imputed date, the imputed date will be changed to the treatment start date.
- 2) A subject not having the particular AE will be censored at the latter of the following two dates: date of last clinic visit, latest AE start date.
- 3) If an AE end date is partial, it will be imputed as follows:
 - a. If all components of the date (day, month and year) are missing, then the end date will be missing.
 - b. If both day and month are missing, then the day and month will be imputed as 31 December.
 - c. If only day is missing, then the day will be imputed as the last day of the corresponding month.

For computing AE duration, partial AE start and end dates will be imputed as previously described, and events with completely unknown (missing) end dates will be censored at the latter of the following two dates: date of last clinic visit, latest AE start date. AE duration is the total number of non-overlapping days for all events per subject, and will be considered censored if any contributing event is censored.

Time to death is defined as (date of death – treatment start date +1). For subjects who do not experience death, time to death is censored at the date of last clinic visit (if missing,

the subject will be censored at the treatment start date).

Special interest adverse events, including MedDRA preferred terms and codes, are presented below in [Table A](#)-[Table D](#):

Table A: Sexual and Breast Adverse Events of Special Interest

Table B: Prostate Cancer Adverse Events of Special Interest

Table C: Cardiovascular Adverse Events of Special Interest

Table D: Infrequent Tier 1 Adverse Events of Special Interest

Table A. Sexual and Breast Adverse Events of Special Interest: MedDRA Preferred Terms and Codes		
Special Interest Event	MedDRA Preferred Term	PT_Code
Altered (Decreased) Libido	Sexual dysfunction	10040477
	Male sexual dysfunction	10057672
	Libido decreased	10024419
	Loss of libido	10024870
	Libido disorder	10061221
Impotence	Erectile dysfunction	10061461
	Organic erectile dysfunction	10052004
	Disturbance in sexual arousal	10058929
	Psychogenic erectile dysfunction	10052005
Ejaculation Disorders	Ejaculation delayed	10014325
	Ejaculation disorder	10014326
	Ejaculation failure	10014328
	Retrograde ejaculation	10038967
	Anorgasmia	10002652
	Orgasm abnormal	10031085
	Premature ejaculation	10036596
	Male orgasmic disorder	10025513
	Orgasmic sensation decreased	10052449
	Semen volume decreased	10039944
Breast Disorders	Breast hyperplasia	10006256
	Breast enlargement	10006242
	Gynaecomastia	10018800
	Nipple disorder	10029417
	Breast engorgement	10006240
	Breast swelling	10006312
	Breast pain	10006298
	Breast tenderness	10006313
	Nipple pain	10029421
	Nipple swelling	10058680
Breast Disorders: Breast Enlargement	Breast discomfort	10049872
	Breast hyperplasia	10006256
	Breast enlargement	10006242
	Gynaecomastia	10018800
	Nipple disorder	10029417
	Breast engorgement	10006240
Breast Disorders: Breast Tenderness	Breast swelling	10006312
	Breast pain	10006298
	Breast tenderness	10006313
	Nipple pain	10029421
	Nipple swelling	10058680
	Breast discomfort	10049872

Table B. Prostate Cancer Adverse Events of Special Interest: MedDRA Preferred Terms and Codes

Special Interest Event	MedDRA Preferred Term	PT_Code
Prostate Cancer	Prostate cancer	10060862
	Prostate cancer stage 0	10036912
	Prostate cancer stage I	10036917
	Prostate cancer stage II	10036918
	Prostate cancer stage III	10036919
	Prostate cancer stage IV	10036920
	Prostate cancer recurrent	10036911
	Prostate cancer metastatic	10036909

Table C. Cardiovascular Adverse Events of Special Interest: MedDRA Preferred Terms and Codes

Special Interest Event	MedDRA Preferred Term	PT_Code
Acute Coronary Syndrome	Acute myocardial infarction	10000891
	Myocardial infarction	10028596
	Silent myocardial infarction	10049768
	Sudden cardiac death	10049418
	Angina unstable	10002388
	Cardiac arrest	10007515
	Cardio-respiratory arrest	10007617
	Cardiac death	10049993
Ischemic Cerebrovascular Events	Acute coronary syndrome	10051592
	Cerebrovascular accident	10008190
	Transient ischemic attack	10044390
	Cerebral infarction	10008118
	Cerebrovascular disorder	10008196
	Cerebral artery embolism	10008088
	Cerebral artery occlusion	10008089
	Cerebral artery thrombosis	10008092
	Ischemic stroke	10061256
	Cerebral circulatory failure	10008097
	Cerebellar infarction	10008034
	Thalamic infarction	10064961
	Reversible ischemic neurologic deficit	10050496
	Thrombotic stroke	10043647
	Embolic stroke	10014498
	Vertebral artery occlusion	10048965
	Carotid arterial embolus	10007684
	Carotid artery occlusion	10048964
	Carotid artery stenosis	10007687
	Carotid artery thrombosis	10007688
	Thrombotic cerebral infarction	10067347
	Brain stem infarction	10006147
	Embolic cerebral infarction	10060839
	Lacunar infarction	10051078
	Brain stem stroke	10068644
	Stroke in evolution	10059613
	Ischaemic cerebral infarction	10060840

Table C. Cardiovascular Adverse Events of Special Interest: MedDRA Preferred Terms and Codes (continued)		
Special Interest Event	MedDRA Preferred Term	PT_Code
Cardiac Failure	Cardiac failure congestive	10007559
	Cardiac failure	10007554
	Left ventricular failure	10024119
	Cardiac failure acute	10007556
	Cardiogenic shock	10007625
	Left ventricular failure acute	10063081
	Right ventricular failure	10039163
	Right ventricular failure acute	10063082
	Ventricular failure	10060953
	Cardiopulmonary failure	10051093
	Congestive cardiomyopathy	10056370
Ischemic Coronary Artery Disorders/ Atherosclerosis	Coronary artery embolism	10011084
	Coronary artery occlusion	10011086
	Coronary artery stenosis	10011089
	Coronary artery thrombosis	10011091
	Myocardial ischemia	10028600
	Coronary artery disease	10011078
	Arteriosclerosis coronary artery	10003211
Cardiac Arrhythmias	Ventricular extrasystoles	10047289
	Torsade de Pointes	10044066
	Ventricular fibrillation	10047290
	Cardiac Fibrillation	10061592
	Pulseless electrical activity	10058151
	Ventricular asystole	10047284
	Long QT syndrome	10024803
	Ventricular tachycardia	10047302
	Ventricular Arrhythmia	10047281
	Ventricular flutter	10047294
Peripheral Vascular Disease	Deep Vein Thrombosis	10051055

Table D. Infrequent Tier 1 Adverse Events of Special Interest: MedDRA Preferred Terms and Codes

Special Interest Event	MedDRA Preferred Term	PT_Code
Relevant for dutasteride:		
Allergic reactions	Anaphylactic reaction	10002198
	Anaphylactic shock	10002199
	Anaphylactic transfusion reaction	10067113
	Anaphylactoid reaction	10002216
	Anaphylactoid shock	10063119
	Circulatory collapse	10009192
	Kounis syndrome	10069167
	Shock	10040560
	Type I hypersensitivity	10045240
	Allergic oedema	10060934
	Angioedema	10002424
	Circumoral oedema	10052250
	Conjunctival oedema	10010726
	Corneal oedema	10011033
	Epiglottic oedema	10015029
	Eye oedema	10052139
	Eye swelling	10015967
	Eyelid oedema	10015993
	Face oedema	10016029
	Gingival oedema	10049305
	Gingival swelling	10018291
	Gleich's syndrome	10066837
	Hereditary angioedema	10019860
	Idiopathic angioedema	10073257
	Idiopathic urticaria	10021247
	Laryngeal oedema	10023845
	Laryngotracheal oedema	10023893
	Limbal swelling	10070492
	Lip oedema	10024558
	Lip swelling	10024570
	Mouth Swelling	10075203
	Oculorespiratory syndrome	10067317
	Oedema mouth	10030110
	Oropharyngeal swelling	10031118
	Palatal oedema	10056998
	Palatal swelling	10074403
	Periorbital oedema	10034545
	Pharyngeal oedema	10034829
	Scleral oedema	10057431
	Swelling face	10042682
	Swollen tongue	10042727
	Tongue oedema	10043967
	Tracheal oedema	10044296
	Urticaria	10046735
	Urticaria cholinergic	10046740
	Urticaria chronic	10052568
	Urticaria papular	10046750
	Acquired epidermolysis bullosa	10056508
	Blister	10005191
	Blister rupture	10073385

Table D. Infrequent Tier 1 Adverse Events of Special Interest: MedDRA Preferred Terms and Codes

Special Interest Event	MedDRA Preferred Term	PT_Code
	Bullous impetigo	10006563
	Conjunctivitis	10010741
	Corneal exfoliation	10064489
	Drug eruption	10013687
	Epidermolysis	10053177
	Epidermolysis bullosa	10014989
	Genital ulceration	10018180
	HLA-B*1502 assay positive	10074771
	HLA-B*5801 assay positive	10074774
	Lip exfoliation	10064482
	Mouth ulceration	10028034
	Mucocutaneous ulceration	10028084
	Mucosa vesicle	10028103
	Mucosal erosion	10061297
	Mucosal exfoliation	10064486
	Mucosal necrosis	10067993
	Mucosal ulceration	10028124
	Nikolsky's sign	10029415
	Noninfective conjunctivitis	10074701
	Oral mucosal blistering	10030995
	Oral mucosal exfoliation	10064487
	Oral papule	10031010
	Oropharyngeal blistering	10067950
	Pemphigoid	10034277
	Pemphigus	10034280
	Penile exfoliation	10064485
	Skin erosion	10040840
	Skin exfoliation	10040844
	Staphylococcal scalded skin syndrome	10041929
	Stomatitis	10042128
	Tongue exfoliation	10064488
	Vaginal exfoliation	10064483
	Vaginal ulceration	10046943
	Vulval ulceration	10047768
	Vulvovaginal rash	10071588
	Vulvovaginal ulceration	10050181
	Application site pruritus	10003053
	Aquagenic pruritus	10003071
	Injection site pruritus	10022093
	Pruritus	10037087
	Pruritus genital	10037093
	Rash pruritic	10037884
	Senile pruritus	10039986
	Itching scar	10050818
	Eyelids pruritus	10051627
	Catheter site pruritus	10052270
	Pruritus generalised	10052576
	Infusion site pruritus	10053664
	Vulvovaginal pruritus	10056530
	Incision site pruritus	10059386
	Uraemic pruritus	10060875
	Pruritus allergic	10063438
	Instillation site pruritus	10063763

Table D. Infrequent Tier 1 Adverse Events of Special Interest: MedDRA Preferred Terms and Codes

Special Interest Event	MedDRA Preferred Term	PT_Code
	Implant site pruritus	10063785
	Cholestatic pruritus	10064190
	Polymorphic eruption of pregnancy	10066100
	Vessel puncture site pruritus	10067254
	Vaccination site pruritus	10068881
	Brachioradial pruritus	10071443
	Notalgia paraesthesia	10072643
Breast Cancer	Apocrine breast carcinoma	10066206
	Invasive breast carcinoma	10075713
	Triple negative breast cancer	10075566
	Breast cancer	10006187
	Breast cancer female	10057654
	Breast cancer in situ	10006189
	Breast cancer male	10061020
	Breast cancer metastatic	10055113
	Breast cancer recurrent	10006198
	Breast cancer stage I	10006199
	Breast cancer stage II	10006200
	Breast cancer stage III	10006201
	Breast cancer stage IV	10006202
	Breast sarcoma	10068582
	Breast sarcoma metastatic	10068583
	Breast sarcoma recurrent	10068584
	Electron radiation therapy to breast	10014437
	Extended radical mastectomy	10015721
	Gamma radiation therapy to breast	10017677
	HER-2 positive breast cancer	10065430
	Inflammatory carcinoma of breast recurrent	10021977
	Inflammatory carcinoma of breast stage III	10021978
	Inflammatory carcinoma of breast stage IV	10021979
	Inflammatory carcinoma of the breast	10021980
	Intraductal papillary breast neoplasm	10073540
	Intraductal proliferative breast lesion	10073094
	Invasive ductal breast carcinoma	10073095
	Invasive lobular breast carcinoma	10073096
	Invasive papillary breast carcinoma	10073098
	Lobular breast carcinoma in situ	10073099
	Malignant nipple neoplasm	10062051
	Malignant nipple neoplasm female	10053129
	Malignant nipple neoplasm male	10053128
	Mastectomy	10026878
	Medullary carcinoma of breast	10027095
	Metaplastic breast carcinoma	10073100
	Modified radical mastectomy	10027799
	Mucinous breast carcinoma	10073101
	Neuroendocrine breast tumour	10073103
	Oestrogen receptor assay positive	10054054
	Oestrogen receptor positive breast cancer	10070577
	Page's disease of nipple	10033364
	Photon radiation therapy to breast	10034949
	Postmastectomy lymphoedema syndrome	10036390

Table D. Infrequent Tier 1 Adverse Events of Special Interest: MedDRA Preferred Terms and Codes

Special Interest Event	MedDRA Preferred Term	PT_Code
	Progesterone receptor assay positive	10054057
	Radical mastectomy	10037773
	Radiotherapy to breast	10062090
	Simple mastectomy	10040700
	Tubular breast carcinoma	10073104
	X-ray therapy to breast	10048199
	Antioestrogen therapy	10002816
	Breast reconstruction	10006305
	Breast neoplasm	10006279
	Nipple neoplasm	10056286
	Phyllodes tumour	10071776
	Biopsy breast abnormal	10004745
	Breast calcifications	10048782
	Breast dysplasia	10006237
	Breast prosthesis implantation	10006303
	Computerised tomogram breast abnormal	10074534
Depressed mood	Activation syndrome	10066817
	Adjustment disorder with depressed mood	10001297
	Columbia suicide severity rating scale abnormal	10075616
	Adjustment disorder with mixed anxiety and depressed mood	10001299
	Agitated depression	10001496
	Anhedonia	10002511
	Antidepressant therapy	10054976
	Childhood depression	10068631
	Decreased interest	10011971
	Depressed mood	10012374
	Depression	10012378
	Depression postoperative	10012390
	Depressive symptom	10054089
	Dysphoria	10013954
	Electroconvulsive therapy	10014404
	Feeling guilty	10049708
	Feeling of despair	10016344
	Feelings of worthlessness	10016374
	Major depression	10057840
	Menopausal depression	10067371
	Post stroke depression	10070606
	Postictal depression	10071324
	Perinatal depression	10078366
	Completed suicide	10010144
	Depression suicidal	10012397
	Intentional overdose	10022523
	Intentional self-injury	10022524
	Poisoning deliberate	10036000
	Self-injurious ideation	10051154
	Suicidal behaviour	10065604
	Suicidal ideation	10042458
	Suicide attempt	10042464

Table D. Infrequent Tier 1 Adverse Events of Special Interest: MedDRA Preferred Terms and Codes

Special Interest Event	MedDRA Preferred Term	PT_Code
Hair changes	Alopecia	10001760
	Alopecia areata	10001761
	Alopecia scarring	10001764
	Alopecia syphilitic	10001765
	Alopecia totalis	10001766
	Alopecia universalis	10001767
	Hypotrichosis	10021126
	Progeria	10036794
	Madarosis	10051235
	Follicular mucinosis	10056506
	Application site alopecia	10059046
	Androgenetic alopecia	10068168
	Satoyoshi syndrome	10070579
	Radiation alopecia	10072045
	Diffuse alopecia	10073736
	Hypertrichosis	10020864
Interference with formation of external genitalia in a male fetus	Congenital vas deferens absence	10010670
	Cryptorchism	10011498
	Epispadias	10015088
	Hypospadias	10021093
	Reproductive tract hypoplasia, male	10057858
	Testicular dysplasia	10059271
	Congenital genital malformation male	10059492
	Penoscrotal fusion	10064951
	Sertoli-cell-only syndrome	10066833
	Buried penis syndrome	10067131
	Penoscrotal transposition	10067287
	Penile torsion	10070235
Potential for decreased male fertility	Infertility tests	10021931
	pH semen	10034784
	pH semen decreased	10034786
	pH semen increased	10034788
	pH semen normal	10034790
	Red blood cells semen	10038176
	Red blood cells semen negative	10038179
	Red blood cells semen positive	10038180
	Semen liquefaction	10039931
	Semen liquefaction normal	10039933
	Semen liquefaction prolonged	10039934
	Semen liquefaction shortened	10039935
	Semen viscosity	10039936
	Semen viscosity decreased	10039938
	Semen viscosity increased	10039940
	Semen viscosity normal	10039942
	Semen volume abnormal	10039943
	Semen volume decreased	10039944
	Semen volume increased	10039946
	Semen volume normal	10039948
	Sperm analysis	10041476
	Sperm analysis abnormal	10041477
	Sperm analysis normal	10041478
	Spermatozoa abnormal	10041498
	Spermatozoa morphology	10041501

Table D. Infrequent Tier 1 Adverse Events of Special Interest: MedDRA Preferred Terms and Codes

Special Interest Event	MedDRA Preferred Term	PT_Code
Testicular pain and swelling	Spermatozoa morphology abnormal	10041502
	Spermatozoa morphology normal	10041503
	Spermatozoa progressive motility abnormal	10041504
	Spermatozoa progressive motility decreased	10041506
	Spermatozoa progressive motility normal	10041507
	White blood cells semen	10047956
	White blood cells semen negative	10047959
	White blood cells semen positive	10047960
	Fructose semen decreased	10052476
	Fructose semen increased	10052477
	Prostatic fluid leukocytes increased	10053866
	Infertility tests abnormal	10062020
	Infertility tests normal	10062021
	pH semen abnormal	10062074
	Semen liquefaction abnormal	10062159
	Semen viscosity abnormal	10062160
	Semen analysis normal	10062238
	Semen analysis	10068482
	Semen analysis abnormal	10068483
	Sperm concentration decreased	10070925
	Sperm concentration increased	10070926
	Sperm concentration abnormal	10070927
	Sperm concentration normal	10070928
	Sperm concentration	10070929
	Sperm concentration zero	10070930
	Total sperm count	10070931
	Total sperm count decreased	10070932
	Infertility	10021926
	Infertility male	10021929
	Anorchism	10002641
	Eunuchoidism	10015532
	Hypogonadism male	10021011
	Testicular atrophy	10043298
	Testicular disorder	10043306
	Testicular failure	10043315
	Testicular failure postoperative	10043317
	Testicular failure primary	10043318
	Testicular hyperfunction	10043334
	Testicular infarction	10043337
	Testicular pain	10043345
	Testicular retraction	10043348
	Testicular swelling	10043354
	Testicular torsion	10043356
	Testicular necrosis	10049572
	Spermatic cord mass	10049792
	Testicular appendage torsion	10050476
	Spermatic cord pain	10051221
	Testicular injury	10051872
	Testicular haemorrhage	10051877
	Epididymal calculus	10052321
	Epididymal enlargement	10052322
	Epididymal tenderness	10052323
	Testis discomfort	10052531

Table D. Infrequent Tier 1 Adverse Events of Special Interest: MedDRA Preferred Terms and Codes

Special Interest Event	MedDRA Preferred Term	PT_Code
	Monorchidism	10055002
	Epididymal disorder	10055045
	Spermatic cord disorder	10056348
	Testicular mass	10058901
	Testotoxicosis	10063654
	Spermatic cord haemorrhage	10065742
	Spermatic cord obstruction	10065805
	Spermatic cord perforation	10065806
	Spermatic cord stenosis	10065807
	Testicular perforation	10065808
	Testicular hypertrophy	10066101
	Testicular oedema	10066769
	Sperm granuloma	10067802
	Testicular microlithiasis	10067829
	Congenital monorchidism	10069505
	Testicular autoimmunity	10071574
Relevant for tamsulosin:		
Atrial fibrillation, tachycardia, arrhythmias	Arrhythmia	10003119
	Heart alternation	10058155
	Heart rate irregular	10019304
	Pacemaker generated arrhythmia	10053486
	Pacemaker syndrome	10051994
	Paroxysmal arrhythmia	10050106
	Pulseless electrical activity	10058151
	Reperfusion arrhythmia	10058156
	Withdrawal arrhythmia	10047997
	Arrhythmia supraventricular	10003130
	Atrial fibrillation	10003658
	Atrial flutter	10003662
	Atrial parasytole	10071666
	Atrial tachycardia	10003668
	Junctional ectopic tachycardia	10074640
	Sinus tachycardia	10040752
	Supraventricular extrasystoles	10042602
	Supraventricular tachyarrhythmia	10065342
	Supraventricular tachycardia	10042604
	ECG P wave inverted	10057526
	Electrocardiogram P wave abnormal	10050384
	Retrograde p-waves	10071187
	Anomalous atrioventricular excitation	10002611
	Cardiac flutter	10052840
	Extrasystoles	10015856
	Tachyarrhythmia	10049447
	Accelerated idioventricular rhythm	10049003
	Cardiac fibrillation	10061592
	Parasytole	10033929
	Rhythm idioventricular	10039111
	Torsade de pointes	10044066
	Ventricular arrhythmia	10047281
	Ventricular extrasystoles	10047289
	Ventricular fibrillation	10047290
	Ventricular flutter	10047294
	Ventricular parasytole	10058184

Table D. Infrequent Tier 1 Adverse Events of Special Interest: MedDRA Preferred Terms and Codes

Special Interest Event	MedDRA Preferred Term	PT_Code
Floppy Iris Syndrome	Ventricular pre-excitation	10049761
	Ventricular tachyarrhythmia	10065341
	Ventricular tachycardia	10047302
Floppy Iris Syndrome	Floppy iris syndrome	10066373
Orthostasis	Dizziness	10013573
	Dizziness postural	10013578
	Orthostatic hypotension	10031127
	Hypotension	10021097
	Syncope	10042772
	Presyncope	10036653
	Blood pressure orthostatic abnormal	10053354
	Blood pressure orthostatic decreased	10053356
Priapism	Priapism	10036661
Stevens-Johnson syndrome	Acute generalised exanthematous pustulosis	10048799
	Cutaneous vasculitis	10011686
	Dermatitis bullous	10012441
	Dermatitis exfoliative	10012455
	Dermatitis exfoliative generalised	10012456
	Drug reaction with eosinophilia and systemic symptoms	10073508
	Epidermal necrosis	10059284
	Erythema multiforme	10015218
	Exfoliative rash	10064579
	Oculomucocutaneous syndrome	10030081
	Skin necrosis	10040893
	Stevens-Johnson syndrome	10042033
	Toxic epidermal necrolysis	10044223
	Toxic skin eruption	10057970

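### Appendix 8 counts an adverse event with no onset date as on-treatment even if it ended before treatment began, and gives it no Kaplan-Meier time

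*SAP*

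**What the plan says.** All the rules stand in Appendix 8 (Section 11.8) and read the same in the original RAP and in Amendment 01.

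- **Period.** An event is on-treatment if its onset is on or after treatment start, "but on or before the treatment stop date, if that is non-missing), or if the onset date is missing". An on-treatment event is also post-randomization.
- **Routes out of the default.** Two rules move an incompletely dated event elsewhere. The route to Pre-Treatment begins "If the non-missing parts of the date (either just year or year/month) are unambiguously before the start of treatment". The route to Post-Treatment reads "If the non-missing parts of the date are unambiguously after the stop of treatment, the AE is considered Post-Treatment". Both look only at the known parts of the onset date.
- **Six-month interval and Kaplan-Meier date.** The algorithm is introduced with "For the purpose of Kaplan-Meier estimates for Special Interest AEs, and for categorizing AEs by time intervals, the following algorithm will be used". Its rule 1a, for an onset with day, month and year all missing, says "then the date will not be imputed, but the AE will be categorized in the first 6-month time period".
- **Censoring.** Rule 2 of the same algorithm says "A subject not having the particular AE will be censored at the latter of the following two dates", namely the last clinic visit and the latest event start date.
- **Onset time.** Time since first dose has formulas for an onset before, or on and after, treatment start, and is "missing otherwise".

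Section 8.2.2 has adverse events recorded from the start of the placebo run-in, and sends pre-treatment events to the listing without summarizing them. Section 8.2.4.3 plans incidence tables, six-month windows and Kaplan-Meier curves for each sexual and breast special-interest event. Sections 8.2.4.4 and 8.2.4.5 extend the same format to prostate cancer and cardiovascular events.

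**The concern.** Two things look wrong. First, the period rule can contradict a date already in the database. An event that ended during run-in cannot have begun on double-blind drug, yet if its onset is blank the rule reports it as on-treatment. Section 8.2.2 treats such events as outside the summaries.

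Second, the incidence tables and the Kaplan-Meier curves for the same Tier 1 event follow rules that do not meet. The tables have an explicit place for an undated event. The curve has none, so whoever programs it must choose whether to drop, censor or date the subject. That choice belongs in the plan, before unblinding.

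**Working it through.** No figure in the SAP bears on this, so the check is a trace of the written rules for an event whose onset date is wholly missing.

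**Case A: the end date is known and falls before double-blind treatment start.**

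1. *Period.* The missing onset alone satisfies the on-treatment definition.
2. *Exit to Pre-Treatment or Post-Treatment.* Both exits need a non-missing part of the onset date. A wholly missing date has none, so neither can apply. The end date is not consulted.
3. *Interval.* Rule 1a places the event in Months 1-6.
4. *Resolution status.* The end date is used here, since "if resolution date is on or before treatment stop date, the AE is considered resolved on-therapy". An end before treatment start is also before treatment stop, so a resolved event is labelled resolved on-therapy. If the stop date is missing, the same label applies unless the action taken was withdrawal of investigational product.
5. *Result.* An event that finished before therapy is summarized as on-treatment, in Months 1-6 and, if resolved, normally as resolved on therapy. Section 8.2.2 would have it listed only.

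**Case B: a special-interest event, the subject's only one of that type, not excluded by its end date.**

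| Output | Rule that applies | What happens to the subject |
|---|---|---|
| Incidence table | on-treatment by default, hence post-randomization | counted as an event |
| Six-month interval table | rule 1a | counted in Months 1-6 |
| Onset time in days | no formula applies | missing |
| Kaplan-Meier event time | rule 1a: date not imputed | none defined |
| Kaplan-Meier censoring time | rule 2: only subjects without the event | does not apply |

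The subject has neither an event time nor a censoring time. Rule 1a is not merely borrowed for the curves: the sentence that opens the algorithm names the Kaplan-Meier estimates as one of its two purposes.

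**How the SAP closes similar gaps.** For efficacy time-to-event endpoints, Appendix 7 states what to do when even the year is unknown: the event is taken as before treatment start. Time to death in Appendix 8 has a fallback when the last clinic visit is missing. The special-interest curves have no equivalent for an undated event.

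**Whether the fix uses existing inputs.** Treatment start date and event end date are both already used in Appendix 8. An event dated to treatment start has, by the SAP's own formula, an onset time of start − start + 1 = day 1, which lies in Months 1-6. It therefore agrees with rule 1a.

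**The case against.** The best defence is that counting a missing onset as on-treatment is deliberate and conservative. Appendix 8 does the same with ambiguous partial dates, and treats a missing causality assessment as drug-related. That stands, and the default should stay. It does not cover Case A, where a recorded date shows the default to be wrong.

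Other limits also stand. Special-interest summaries use post-randomization events unless otherwise indicated (Section 8.2.4.2), so confusing on-treatment with post-treatment does not change their totals; only the run-in case does. That case needs an onset not known even to the year, together with a known early end date. Database cleaning precedes the freeze (Section 3.2), and all events appear in Listings 3.2 and 3.3. Section 8.2 also relies on a Program Safety Analysis Plan that is not shown, which might address the point.

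Three stronger readings are tempting and not supported:

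- *The subject drops out of the curve, so the curves understate risk.* The SAP does not say whether he is dropped, censored or given an event time. A man with another dated event of the same type could still have a time.
- *The onset tables are loaded towards the first six months and suggest that events stop.* This would need many undated events, and no count is given.
- *An event first recorded late, for instance at Month 24, should be placed by its recording visit.* The SAP mentions no visit-of-first-entry variable. Nor is the preceding visit a true lower bound, since an event reported late may have begun earlier.

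**Conclusion.** The point holds as a minor one. Two results follow directly from the written rules: an undated event known to have ended before treatment start is summarized as on-treatment in Months 1-6, and a subject whose only special-interest event of a type is undated is counted in the tables with no defined Kaplan-Meier time.

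Each affected event changes a count, or leaves a curve undefined, for one subject. The total cannot be estimated because the SAP does not give the number of wholly undated events; it is probably small. The direction of any bias in the curves cannot be stated either, since their handling is unspecified. The Kaplan-Meier displays carry no planned test, so no formal conclusion depends on them. The conclusion assumes that no rule outside this document overrides Appendix 8.

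**What to change.** Add two sentences to Appendix 8.

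1. An event with a wholly missing onset date is Pre-Treatment when its known end date is before treatment start; otherwise the on-treatment default applies as now. A partial end date can be used as imputed under rule 3, which takes the last day of the month or 31 December, so an event is reclassified only when its latest possible end is before treatment start.
2. For the Kaplan-Meier analysis of special-interest events, each remaining wholly undated event receives one stated event time consistent with its Months 1-6 placement, for example the treatment start date. Because that choice makes the undated event the first one in a man who also has a dated event of the same type, the text should say whether this is intended.

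The curves and tables then count the same subjects. The cost is the two sentences and a small change to the derivation program. No new data are needed, since treatment start and event end dates are already used in Appendix 8.
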